5.4. Pharmacokinetic Parameters Population

The PK Population will comprise all randomized subjects who receive any amount of LSALT, have sufficient concentration data to support accurate estimation of at least 1 PK parameter (determined at the discretion of the pharmacokineticist in consultation with the Sponsor) and will be based on the actual treatment received, if this differs from that to which the subject was randomized. Subjects who receive only placebo will be excluded from the PK Parameters Population. The PK Parameters Population will be used for the summaries/analyses of all PK parameter data.

5.5. Protocol Deviations

Subject data will be examined for evidence of protocol deviations in order to assess how well the protocol was followed. Possible protocol deviations will be independently reviewed and acknowledged by Arch Biopartners Inc.

All protocol deviations will be detailed in the listings.

This document is confidential.

6. General Aspects for Statistical Analysis

6.1. General Methods

SAS® for Windows, Release 9.4 (SAS® Institute Inc., Cary, NC, USA) software will be used to perform all data analyses.

All data in the database will be presented in the data listings. Unless otherwise stated, all listings will be sorted by cohort, randomized treatment group, subject number and assessment date/time. For the purposes of the summary tables, all subjects randomized to placebo will be combined into a single placebo group.

All listings and summaries/analyses will be presented separately for each study part. Unless otherwise stated, the descriptions of the analyses which follow, apply to both SAD/MAD study parts (Low Dose subjects' results will be listed only).

The following labels for treatment will be used on all tabulations where the results are displayed by treatment, in the following order:

SAD:

- All Placebo
- LSALT 1.0 mg
- LSALT 2.5 mg
- LSALT 5.0 mg

MAD:

- All Placebo
- LSALT 1.0 mg
- LSALT 2.5 mg
- LSALT 5.0 mg

Summary Statistics:

Unless otherwise stated, continuous variables will be summarized using the number of observations (n), and the statistics mean, median, standard deviation (SD), minimum and maximum. The minimum and maximum values will be presented to the same number of decimal places as recorded in the case report form (CRF), mean and median will be presented to one more decimal place than the raw data and the SD will be presented to two more decimal places than the raw data. Summaries of change-from-baseline variables will include only subjects who have both a baseline value and corresponding value at the timepoint of interest. Categorical variables will be summarized with frequency counts and percentages. Percentages will be rounded to one decimal place, with the denominator being the number of subjects in the relevant population, unless otherwise stated.

This document is confidential.

For the plasma PK data, the data will be rounded to two decimal places in the listings. Summary statistics will also include the geometric mean (three decimal places) and geometric coefficient of variation (CV) (%) (four decimal places). The geometric mean and CV(%) will not be calculated for T_{max} , $t_{1/2}$, $\%AUC_{exp}$ and λ_z .

Only data from nominal protocol scheduled visits will be included in the summary tables. Data from unscheduled visits will not be included in the summary tables (unless they were used as baseline) but will be included in the listings and figures.

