Female and male participants (along with their female partners) are required to use a method of acceptable contraception, including one barrier method (condom) and one additional highly effective method (i.e., hormonal contraceptive, intra-uterine device) or abstinence for the duration of the study for 90 days following the last dose of study drug.

7.3.8 Duration of Follow-up. Participants are evaluated for adverse events for 72 hours and 6 days after receiving the low dose and single dose of study drug respectively. Patients receiving multiple daily dosing are evaluated for 17 days after receiving the last dose of the LSALT peptide. Participants with adverse events will be followed until resolution or stabilization of the adverse event. Follow-up after the conclusion of the study participation will be per routine clinical care.

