4.1. Safety Endpoints (Primary)

The primary safety endpoints are:

- Incidence of AEs.
- Clinical laboratory test results (hematology, chemistry, coagulation and urinalysis).
- Vital sign measurements
- 12 lead electrocardiogram (ECG) readings

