6.2. Key Definitions

Baseline:

In general, baseline will be defined for each subject and will be defined as the last available, non-missing assessment results obtained prior to first study drug administration. Unknown, Not Done, Not Applicable and other classifications of missing data will not be considered when calculating baseline observations. However, valid categorical observations will be considered for baseline calculations.

Study Day:

Study day will be calculated using first study drug administration date as the reference date. If the date of interest occurs on or after the first study drug administration date, study day will be calculated as (date of interest – first study drug administration date) + 1. If the date of interest occurs prior to the first study drug administration date, study day will be calculated as (date of interest – first study drug administration date). There will be no study day 0.

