10.3. Laboratory Evaluations

Laboratory data (hematology, chemistry and coagulation) will be summarized at each protocol-scheduled visit, by actual treatment. Actual values and actual changes from baseline will be presented.

In addition, a shift table representing the categorical change in laboratory results interpretation (normal, abnormal not clinically significant, or abnormal clinically significant) from baseline to each post baseline visit will be presented.

This document is confidential.

Urinalysis results evaluation will be summarized at each protocol-scheduled timepoint, by actual treatment, using frequency tabulations.

High and low/abnormal results will be flagged in the listings.

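### Laboratory, vital-sign and ECG abnormalities seen only at unscheduled post-dose assessments are left out of the by-dose summary and shift tables

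*SAP*

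**What the plan says.** **Endpoints.** SAP 4.1 names "Clinical laboratory test results (hematology, chemistry, coagulation and urinalysis" among the primary safety endpoints, together with vital signs, 12-lead ECG and the incidence of adverse events.

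**Table rule.** SAP 6.1 states "Only data from nominal protocol scheduled visits will be included in the summary tables", and then "Data from unscheduled visits will not be included in the summary tables (unless they were used as baseline". The second sentence goes on to say that unscheduled data are left out of the tables "but will be included in the listings and figures". The same section also promises "All data in the database will be presented in the data listings".

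**Shift tables.** SAP 10.3 plans laboratory shifts across three categories (normal, abnormal not clinically significant, abnormal clinically significant) "from baseline to each post baseline visit will be presented". SAP 10.4 and 10.5 do the same for vital signs and ECG. The shells in SAP 16 tell the programmer to continue for protocol-scheduled visits and timepoints. SAP 6.4 applies no visit windows.

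**Baseline.** SAP 6.2 takes the "last available, non-missing assessment results obtained prior to first study drug administration", so an unscheduled pre-dose value may serve.

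**Follow-up.** Protocol 7.3.8 states "Participants with adverse events will be followed until resolution or stabilization of the adverse event".

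**The concern.** Three of the four primary safety endpoint groups are reported by dose through tables that cannot show an unscheduled post-dose result. Such tests are usually ordered because something looked wrong, or to follow an event already under way, so the excluded results are unlikely to be a neutral sample.

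The risk is a contradiction inside the study report: a by-dose shift table with no clinically significant change, beside a listing that contains one. A reader who relies on the tables for the safety conclusion would not see it. Dose escalation is not directly at stake, because Protocol 8.0 rests that on Safety Review Committee meetings and adverse events rather than on the final tables.

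**Working it through.** **1. Plan figures.** The point disputes no stated number. Enrolment reproduces: 4 + 3 × 8 + 3 × 8 = 52 (Protocol 6.3). Each cohort of 8 at 3:1 gives 8 × 3/4 = 6 active and 2 placebo (Protocol 5.0).

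**2. Trace one result through the SAP.** Suppose a clinically significant value is found at an unscheduled post-dose visit.

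- By-visit summary: excluded by SAP 6.1.
- Shift table: excluded, because its visits are the scheduled ones.
- Reassignment to a nearby scheduled visit: not possible, because SAP 6.4 applies no windows.
- Worst-post-baseline or any-time table: none is planned in SAP 10 or the shells.
- Figures: every figure listed in SAP 16 is a pharmacokinetic figure, so none shows safety data.
- Listings: included and flagged.
- TEAE tables: included only if reported as an adverse event. SAP 10.2 defines these by onset after first dose, so visit timing does not matter.

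**3. Where scheduled testing leaves gaps** (Protocol 7.1.4 and 7.2.5 timetables).

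| Data | Scheduled post-dose | Days without a scheduled test |
|---|---|---|
| SAD coagulation | Day 2 | Days 3-7 |
| SAD chemistry and CBC, timetable | Days 2, 7 | Days 3-6 |
| SAD chemistry and CBC, Protocol 7.3.6 | Days 2, 4, 7 | Days 3, 5-6 |
| MAD chemistry and CBC | Days 2, 4, 7, 14, 21 | Days 3, 5-6, 8-13, 15-20 |
| MAD coagulation | Days 2, 4, 7 | Days 3, 5-6, 8-21 |
| MAD ECG | Days 1-4, 21 | Days 5-20 |

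A SAD coagulation abnormality that begins after the Day 2 sample can never enter a table, whatever its duration. Dosing-day coverage is good by contrast: vital signs pre-dose and at 1, 2, 6 and 10 hours, ECG pre-dose and at 2 and 8 hours. In SAD both are repeated on Days 2, 4 and 7.

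**4. Size of one omission.** For one dose group, with exact (Clopper-Pearson) two-sided 95% limits:

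- Shown: 1/6 = 16.7%, limits 0.4% to 64.1%. The lower limit is 1 − 0.975^(1/6) = 0.4%.
- Omitted: 0/6 = 0%, upper limit 1 − 0.025^(1/6) = 45.9%.

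The SAP plans no intervals for safety data; these only show the scale.

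**5. Illustration of the laboratory gaps.** Assume onset uniform from Day 1 to the last visit and a duration of 1, 2 or 3 days. The documents give neither. The share touching no scheduled laboratory day is 1 − (onset days that reach a scheduled test)/(days in the period):

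- SAD, Days 2 and 7 (6-day period): 1 − 2/6 = 67%; 1 − 3/6 = 50%; 1 − 4/6 = 33%.
- SAD, Days 2, 4 and 7: 1 − 3/6 = 50%; 1 − 5/6 = 17%; 1 − 6/6 = 0%.
- MAD, Days 2, 4, 7, 14 and 21 (20-day period): 1 − 5/20 = 75%; 1 − 9/20 = 55%; 1 − 12/20 = 40%.

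These are abnormalities that scheduled sampling alone would not meet. A recorded result is lost from the tables only where an unscheduled test was actually done.

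**The case against.** A reader might infer that these abnormalities vanish from the primary safety summaries. The documents do not support that. The listings hold every result and flag the abnormal ones. An abnormality reported as an adverse event counts in the TEAE tables, and adverse-event incidence is itself a primary safety endpoint. The follow-up in Protocol 7.3.8 applies to participants who already have an adverse event, so on that route the event should already be counted if it began after dosing. Protocol 7.3.5 monitors for adverse effects with these same tests, and the grading in Protocol 9.2 lets Grade 1 cover diagnostic observations alone. This all stands and narrows the gap. It does not close it, because no passage says which abnormal results must be recorded as adverse events.

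A reader might also infer a one-sided rule, since an unscheduled value can set baseline but cannot count as a shift. Taking the last pre-dose value is ordinary practice with no evident direction of bias. Unscheduled tests also include repeats that come back normal; leaving those out keeps the scheduled abnormal value in the table.

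Two further limits are fair. Sparse scheduling does not describe dosing-day vital signs or ECG. An example built on an unscheduled SAD Day 4 chemistry sample would also be unsafe: the timetable omits Day 4 chemistry and CBC, but Protocol 7.3.6 schedules them.

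Finally, Protocol 16.0 promised only listings with clinical-significance comments for laboratory values, and with 24 participants per part the listings can be read in full. That lowers the importance of the point, but it does not stop a table from disagreeing with its own listing.

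**Conclusion.** The point holds in a limited form. If the SAP is followed exactly, an abnormality seen only at an unscheduled post-dose assessment is absent from the by-dose laboratory, vital-sign and ECG summary and shift tables. It is found only in the flagged listings unless it is also reported as an adverse event.

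One such result changes a dose group from 1/6 to 0/6. That size assumes such a result occurs and is not reported as an adverse event; the documents give no rate of unscheduled testing, so no expected number can be stated. The gap is clearest for laboratory tests and for MAD ECG after Day 4. This is a cheap improvement to a descriptive analysis, and it gives no reason to change the baseline definition.

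**What to change.** - Keep all by-visit summaries on scheduled data.
- In the shift tables of SAP 10.3, 10.4 and 10.5, add one row per parameter from baseline to the worst post-baseline interpretation (Normal < Abnormal NCS < Abnormal CS), using all scheduled and unscheduled post-dose results. Update the SAP 16 shells to match.
- Exempt that row from the table rule in SAP 6.1.
- Footnote that participants with more unscheduled tests have more chances of an abnormal value.
- Reconcile the SAD timetable with Protocol 7.3.6 on Day 4 chemistry and CBC, so that it is clear which results count as scheduled.

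The cost is SAP wording and one extra row per parameter in tables already planned. The data are already collected and listed. The one drawback is unequal testing frequency, which the footnote discloses.

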6.2. Key Definitions

Baseline:

In general, baseline will be defined for each subject and will be defined as the last available, non-missing assessment results obtained prior to first study drug administration. Unknown, Not Done, Not Applicable and other classifications of missing data will not be considered when calculating baseline observations. However, valid categorical observations will be considered for baseline calculations.

Study Day:

Study day will be calculated using first study drug administration date as the reference date. If the date of interest occurs on or after the first study drug administration date, study day will be calculated as (date of interest – first study drug administration date) + 1. If the date of interest occurs prior to the first study drug administration date, study day will be calculated as (date of interest – first study drug administration date). There will be no study day 0.

6.3. Missing Data

All withdrawals will be included in all summaries up to the time of withdrawal.

There will be no imputation for missing data, unless otherwise specified.

6.4. Visit Windows

All assessments will be included in the listings. No visit windows will be applied to assessments.

This document is confidential.

7. Demographic and Baseline Characteristics

7.1. Subject Disposition and Withdrawals

Subject enrollment and disposition, including reasons for early withdrawal from the study, will be summarized by randomized treatment.

All subject disposition parameters will be presented for individual subjects in the listings.

7.2. Demographic and Baseline Characteristics

Demographic and baseline characteristics (including gender, child bearing potential, age, race, ethnicity, height, weight and body mass index [BMI]) will be summarized by randomized treatment and overall.

All demographic and baseline characteristics (and other screening data) will be listed.

7.3. Medical History

Medical history, urine drug screen and alcohol breath test will be listed only.

This document is confidential.

8. Analysis Of Pharmacokinetics

All plasma concentration summaries will be conducted on the PK Concentration Population. All plasma PK parameter summaries/analyses will be conducted on the PK Parameters Population.

8.1. PK Sampling Schedule

SAD:

PK blood samples: 5 ml of blood will be drawn at 30 minutes pre (+/- 5 minutes) and 15 minutes (+/- 5 minutes), 30 minutes (+/- 5 minutes), 45 minutes (+/- 5 minutes), 1h (+/- 5 minutes), 2h (+/- 5 minutes), 4h (+/- 10 minutes), 6h (+/- 10 minutes), 8h (+/- 10 minutes), and 12h (+/- 30 minutes) after the LSALT infusion has completed; followed by 24h and 72h samples.

MAD:

Day 1 PK blood samples: 5 ml of blood will be drawn at 30 minutes pre start of infusion (+/- 5 minutes) and 15 minutes (+/- 5 minutes), 30 minutes (+/- 5 minutes), 45 minutes (+/- 5 minutes), 1h (+/- 5 minutes), 2h (+/- 5 minutes), 4h (+/- 10 minutes), 6h (+/- 10 minutes), 8h (+/- 10 minutes), and 12h (+/- 30 minutes) after the LSALT infusion has completed; followed by 24h sample.

Day 3 PK blood samples: 5 ml of blood will be drawn at 15 minutes (+/- 5 minutes), 30 minutes (+/- 5 minutes), 45 minutes (+/- 5 minutes), 1h (+/- 5 minutes), 2h (+/- 5 minutes), 4h (+/- 10 minutes), 6h (+/- 10 minutes), 8h (+/- 10 minutes), and 12h (+/- 30 minutes) after the 3rd LSALT infusion has completed; followed by 72h and 92h samples.

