3.5 Drug Metabolism and Pharmacokinetics

Plasma levels of LSALT peptide were measured post-intravenous dosing of 100, 250 and 450 mg/kg in rats. Terminal elimination half-lives of 0.66 – 1.17 hr and MRT_{obs} values of 0.58 – 0.85 hr were observed for LSALT peptide. The AUC_{0- ∞} was linear and close to proportional with dose.

LSALT peptide is stable in human plasma for up to 90 minutes with no detectable metabolic/proteolytic fragments as measured by mass spectrometry. LSALT peptide is undetectable in whole blood in the absence of phosphoric acid due to red or white blood cell binding. In human whole blood, 90% or more of the LSALT peptide is contained within the cellular compartment. LSALT peptide however is compatible with blood and does not induce red blood cell hemolysis. Work is ongoing to identify LSALT peptide volume of distribution, tissue biodistribution, and excretion.

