Study Day	Screen -29 to -2	-1	1	2	4	7
In patient period		X	X			
Informed consent	X					
Vital signs	X	X	X ⁴	X	X	X
Physical Exam	X	X		X	X	X
Alcohol Breath Test	X	X				
Drugs of Abuse ⁶	X	X				
Urinalysis	X	X		x		X
CBC	X	X		X		X
Chemistry	X	X		X		X
Creatine/eGFR	X	X		X		X
LFTs	X	X		X		X
PK			X ¹	X ²	X ³	X
INR/PTT	X			X		
CXR	X					X
ECG	X	X	X ⁵	X	X	X
B-hCG ⁷	X	X				X
Adverse Event	X	X	X	X	X	X
LSALT Administration			X			
Discharge from unit				X		
Follow up					X	X

Note: Fasting for blood sampling required for Screening and post dose Follow up. Participants will be required to have fasted from all food and drink except water for at least 8 hours prior to blood sampling.

1. PK blood samples: 5 ml of blood will be drawn at 30 mins pre (+/- 5 mins) and 15 mins (+/- 5 mins), 30 mins (+/- 5 mins), 45 mins (+/- 5 mins), 1h (+/- 5 mins), 2h (+/- 5 mins), 4h (+/- 10 mins), 6h (+/- 10 mins), 8h (+/- 10 mins), and 12h (+/- 30 mins) after the LSALT infusion has completed
2. PK blood sample: 24 hours (+/- 30 mins) after infusion has completed
3. PK blood sample: 72 hours (+/- 30 mins) after Infusion has completed

4. Vital signs dosing day (seated): pre dose within 30 mins prior to infusion start), 1 hour (+/- 10mins), 2 hour (+/- 10 mins) 6 hours (+/- 15min) and 10 hours post completion of infusion (+/- 30 mins)
5. 12 lead electrocardiogram (supine): pre dose (+/- 30 mins), 2 hours (+/- 15 mins) and 8 hours post completion of infusion (+/- 30 mins)
6. Repeat Drugs of Abuse (DoA) is permitted at the discretion of the Investigator
7. Pregnancy test will be via serum B-hCG at Screening and a urine pregnancy test at pre dose (Study Day -1/Day 12) and follow up

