10.1.6 Administration

LSALT peptide is diluted in 100 ml of 0.9% sodium chloride and administered intravenously over 2 hours ± 5 minutes. Based upon evaluation of tolerability and safety of the first cohort, and consistent with the adaptive design, infusion rates could be increased or decreased for subsequent cohorts, as determined by the SRC.

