8.2. Derived PK Parameters

SAD:

The following plasma PK parameters will be derived for the SAD study portion.

Parameter	Definition	Method of Determination
AUC ₀₋₂₄	Area under the plasma concentration-time curve, from time 0 to 24 hours.	Linear trapezoidal method
AUC ₀₋₁₂	Area under the plasma concentration-time curve, from time 0 to 12 hours.	Linear trapezoidal method
AUC _{0-t}	Area under the plasma concentration-time curve, from time 0 to the last measurable concentration.	Linear trapezoidal method
AUC _{0-inf}	Area under the plasma concentration-time curve, from time 0 extrapolated to infinity.	AUC _{0-t} + C _{last} /λ _z , where C _{last} is the last measurable concentration.
%AUC _{exp}	Percentage of AUC _{0-inf} due to extrapolation from the time of last concentration to infinity.	(1 - AUC _{0-t} /AUC _{0-inf}) * 100

This document is confidential.

Parameter	Definition	Method of Determination
C_{max}	Maximum observed plasma concentration.	Observed directly from data
T_{max}	Time to reach C_{max} . If the maximum value occurs at more than 1 timepoint, T_{max} is defined as the first timepoint with this value.	Observed directly from data
$t_{1/2}$	Apparent first-order terminal elimination half-life.	$\ln(2)/\lambda_z$
λ_z	Apparent first-order terminal elimination rate constant.	Estimated by linear regression of the terminal elimination phase of the log-linear drug concentration-time curve
Cl/F	Apparent total body clearance.	Estimated as Dose/AUC _{0-inf}
V_z/F	Apparent volume of distribution.	Estimated as Dose/(\mathbf{\lambda}_z \times AUC_{0-inf})

MAD:

The following plasma PK parameters will be derived for the MAD study portion, for Day 1 and Day 3.

Parameter	Definition	Method of Determination
AUC_{0-24}	Area under the plasma concentration-time curve, from time 0 to 24 hours. (Day 1)	Linear trapezoidal method
AUC_{0-12}	Area under the plasma concentration-time curve, from time 0 to 12 hours. (Day 1)	Linear trapezoidal method
AUC_{0-tau}	Area under the curve over a dosing interval at steady state (Day 3 only)	Linear trapezoidal method
AUC_{0-t}	Area under the plasma concentration-time curve, from time 0 to the last measurable concentration.	Linear trapezoidal method
AUC_{0-inf}	Area under the plasma concentration-time curve, from time 0 extrapolated to infinity.	$AUC_{0-t} + C_{last}/\lambda_z$, where C_{last} is the last measurable concentration.

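### On the SAP's end-of-infusion sampling times, the linear trapezoid reduces the whole 2 h infusion to one triangle; at half-lives like the rat values, AUC comes out about 13-29% low and clearance about 15-41% high

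*SAP*

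**What the plan says.** **Sampling.** For SAD, SAP 8.1 lists draws at "30 minutes pre (+/- 5 minutes) and 15 minutes (+/- 5 minutes), 30 minutes (+/- 5 minutes), 45 minutes (+/- 5 minutes" and so on, ending "and 12h (+/- 30 minutes) after the LSALT infusion has completed; followed by 24h and 72h samples". Footnote 1 to the SAD timetable in Protocol 7.1.4 uses the same reference point: "and 12h (+/- 30 mins) after the LSALT infusion has completed". The SAD and MAD concentration listing shells also put the first post-dose sample 15 minutes after the end of infusion. SAP 8.1 uses the end-of-infusion reference for MAD Day 1 and Day 3 as well.

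**Infusion.** Protocol 10.1.6 has the drug "administered intravenously over 2 hours ± 5 minutes".

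**Analysis.** In SAP 8.2 the method for AUC0-12, AUC0-24 and AUC0-t is the "Linear trapezoidal method". AUC0-t is the "Area under the plasma concentration-time curve, from time 0 to the last measurable concentration", and AUC0-inf adds Clast/λz to it. Cl/F is Dose/AUC0-inf and Vz/F is Dose/(λz × AUC0-inf). SAP 8.3 sets values below the quantification limit to missing once a measurable concentration has been seen. Nothing in 8.2 or 8.3 deals with an unsampled infusion period.

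**Other sampling clocks.** The SAD Day 1 text in Protocol 7.1.4 counts samples from the start of infusion, which puts several inside it. Protocol 7.3.6 lists dense times from infusion onset, and Protocol 7.2.5 does the same for MAD. Protocol 15.0 gives a further set of times. SAP 12 declares no changes from the protocol.

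**Half-life.** Protocol 3.5 reports, in rats, "Terminal elimination half-lives of 0.66 – 1.17 hr". No human value appears.

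**The concern.** During a constant-rate infusion of a short half-life drug, concentration rises steeply, flattens, peaks when the infusion stops at 2 h, and is already falling by 2.25 h. A straight line from zero at the start to the 2.25 h value lies below that curve throughout. The lost area goes into every AUC that starts at time 0, and from there into Cl/F and Vz/F.

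Pharmacokinetics is the secondary objective, and 18 active SAD participants (3 cohorts of 6) would be affected. The 18 active MAD participants would be too, if they were sampled on the SAP schedule. No planned output would reveal the problem: %AUCexp describes only the extrapolated tail, not the front of the curve. Observed Cmax is low for the same reason.

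**Working it through.** The documents state no AUC, clearance or half-life for humans, so there is no plan figure to reproduce. The check applies the SAP's rules to a known curve.

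**Inputs**
- Infusion length 2 h (Protocol 10.1.6).
- SAP 8.1 SAD times converted to hours from infusion start: 2.25, 2.5, 2.75, 3, 4, 6, 8, 10, 14, 26, 74.
- Time 0 taken as infusion start with concentration 0. This is an assumption; the SAP does not define it.
- Half-lives 0.66-1.17 h (rat, Protocol 3.5). Using these for humans is an assumption, so a wider range is shown below.
- Assay limit not given; varied from 5% to 0.1% of the true peak (assumption).
- One compartment, no noise (assumption).

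**Formulas**, with concentration in units of infusion rate/CL and k = ln 2/half-life:
- up to 2 h: C(t) = 1 - exp(-kt)
- after 2 h: C(t) = C(2) × exp(-k(t - 2))
- true AUC0-inf = 2
- triangle for 0-2.25 h = 0.5 × 2.25 × C(2.25)
- true area for 0-2.25 h = 2 - C(2.25)/k

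**Step 1: the infusion segment**

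| Half-life (h) | k | C(2.25) | Triangle | Truth | Error |
|---|---|---|---|---|---|
| 0.66 | 1.050 | 0.675 | 0.759 | 1.357 | -44% |
| 0.85 | 0.815 | 0.656 | 0.738 | 1.196 | -38% |
| 1.17 | 0.592 | 0.599 | 0.673 | 0.990 | -32% |

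**Step 2: the whole curve.** On the falling limb the linear trapezoid overstates, which gives a little back. As shares of true AUC0-inf, with the assay limit at 1% of peak:
- 0.66 h: the triangle gives 38.0% against 67.9%, a loss of 29.9 points; the falling limb returns 2.5; net -27.4%.
- 1.17 h: 33.7% against 49.5%, a loss of 15.8 points; the falling limb returns 2.3; net -13.5%.

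**Step 3: clearance**, error = 2/AUC0-inf - 1:
- 0.66 h: 2/1.452 - 1 = +38%
- 0.85 h: 2/1.590 - 1 = +26% (AUC0-inf -20.5%)
- 1.17 h: 2/1.730 - 1 = +16%

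Vz/F carries the same relative error when λz is right. Across assay limits of 5% to 0.1%, AUC0-inf is -27% to -29% at 0.66 h (CL +37% to +41%) and -13% to -14% at 1.17 h (CL +15% to +16%). AUC0-12 and AUC0-24 show the same errors at these half-lives. Observed Cmax is 14-23% below the end-of-infusion peak.

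**Step 4: other half-lives (AUC0-inf)**
- 0.25 h: about -63%
- 2 h: about -6%
- 3 h: -1% to -4%
- sign change: between about 3.4 and 5.6 h, depending on the assay limit
- 6 h: +1% to +11%, the upper end only if the assay still quantifies the 72 h sample

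Two-compartment curves gave both signs: -22% to -46% for half-lives of 0.25/1.17 h, and -1.8% to +7.2% for 0.66/6 h with equal coefficients.

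**Step 5: is the gap the cause?** Adding hypothetical samples at 0.5, 1, 1.5 and 2 h from the start to the SAP times brings the AUC0-inf error to between +0.1% and +2.1% at 0.66-1.17 h.

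**The case against.** Four objections have weight.

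1. **The direction is not guaranteed.** A reader might infer that every SAD AUC is too low and every clearance too high. The documents do not support that. Only the infusion triangle has a fixed sign; the falling limb errs the other way, and above a half-life of about 3.4-5.6 h the total can reverse. The only half-lives given come from rats at 100-450 mg/kg. This stands, and the finding is conditional on half-life.

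2. **The sampling clock is unsettled.** If SAD samples followed the start-of-infusion times in the Protocol 7.1.4 Day 1 text, the same calculation at 0.66-1.17 h gives AUC0-inf about +5% to +13%, the opposite sign. This stands. Protocol 3.7 says the first six cohorts are complete, so actual times exist and should be established first.

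3. **SAD against MAD.** A reader might infer that SAD and MAD Day 1 AUCs at the same dose will differ through sampling alone. That follows only if SAD used the SAP times and MAD used the Protocol 7.2.5 times. Within the SAP both share the gap, and SAP 6.1 presents the study parts separately.

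4. **A model fit is not automatically better.** It is tempting to make a compartment fit the main result. With two-compartment truth (0.66/6 h, 90/10 coefficients), a one-compartment fit gave AUC0-inf errors of -14% to -31% depending on weighting and assay limit, against about -13% for the trapezoid. This stands, and limits the fit to a sensitivity analysis.

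It is also fair that the PK analysis is descriptive and unpowered. Under linear kinetics the relative error is the same at each dose if the same points stay quantifiable, so the dose-proportionality slope in SAP 8.4 is largely unaffected. The absolute AUC, CL, Vz and Cmax are what suffer.

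**Conclusion.** The concern holds in conditional form. On the SAP 8.1 end-of-infusion schedule, for SAD and for MAD Days 1 and 3, the linear trapezoid replaces the infusion with one triangle. If the human half-life resembles 0.66-1.17 h and one compartment is adequate, AUC0-inf is about 13-29% low and CL about 15-41% high. The error is modest by 2 h and can change sign above about 3.4 h. The result rests on three things the documents leave open: the human half-life, the assay limit, and which sampling clock was used. It is worth correcting before the final analysis because the remedy is cheap and the planned output would not show the bias.

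**What to change.** 1. Reconcile the SAD Day 1 text and timetable footnote 1 in Protocol 7.1.4 with Protocol 7.3.6, Protocol 15.0 and SAP 8.1 on whether samples count from the start or end of infusion. Do the same for MAD between Protocol 7.2.5 and SAP 8.1. Establish the actual sample times from the collected data, and update SAP 12.
2. Add to SAP 8.2: for any profile with no sample during the infusion, fit a constant-rate infusion model in Phoenix WinNonlin using actual dose, actual infusion duration and actual sample times. State in advance the criterion for one versus two compartments and the weighting. Report its CL, V, AUC0-inf and end-of-infusion concentration beside the trapezoidal values as a sensitivity analysis.
3. Footnote the trapezoidal AUC, Cl/F and Vz/F for those profiles as biased by the unsampled infusion period, with AUC low if the half-life is short. Do not compare them with AUCs from profiles sampled during infusion.

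Cost: SAP wording and one modelling step per affected profile, in software SAP 14 already names. No new blood samples are needed. The downside is that the added estimates depend on the compartment model.
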